7.1.1 Safety Follow-up Evaluation

Subjects discontinuing from treatment for any reason will have 2 safety follow-up visits, at 30 days (+5 days) and 60 days (\pm 7 days) after the last trial treatment administration, respectively. If the subject initiates new anticancer treatment within 30 days of the last trial treatment administration, the safety follow-up visit should be performed prior to starting new anticancer treatment. Once new anticancer treatment is initiated, the subject will move into survival status follow-up (see Section 7.1.2).

7.1.2 Survival Status

Survival status will be assessed every 12 weeks (\pm 14 days), beginning from the day the subject receives the last trial treatment administration and continuing until the subject dies, withdraws consent for survival status follow-up, or the trial ends. Subjects may be contacted by telephone, email, or visit. Subjects who are not available, or whose designated family members are not available, for this assessment should be entered as "lost to follow-up" (see Section 7.3 and Section 6.8). In the monotherapy dose escalation part, there will be no survival follow-up for the last subject discontinuing treatment.

Site personnel, or an independent third party, will attempt to collect the survival status of the subject within legal and ethical boundaries for all subjects enrolled. Survival status may be collected through medical records, national registries, or publicly available information as allowed per local regulation. If survival status is determined as deceased, this will be documented.

7.2 Subject Withdrawal From the Trial

A subject will be withdrawn from the trial for any of the following reasons:

- Death
- Lost to follow-up
- Sponsor decision
- Subject withdraws consent
- Maximum trial duration met

When a subject withdraws before completing the trial, the reason for withdrawal is to be documented.

During both the monotherapy Dose Escalation phase 1a and the combination therapy Dose Escalation phase 1b, subjects who withdraw before the end of the DLT period may be replaced. These replacement subjects will be assigned to the same treatment cohort as the subjects they are replacing.

If a subject discontinues trial treatment and withdraws from the trial before PD, the treatment discontinuation visit assessments should be obtained whenever possible. If the reason for withdrawal from the trial is withdrawal of consent, then no additional assessments are allowed, but the sponsor may retain and continue to use any data collected before such a withdrawal of the consent.

When a subject withdraws before completing the trial, the reason for withdrawal is to be documented.

If a subject withdraws from the trial, he/she may request destruction of any samples taken and not tested, and the investigator must notify the sponsor accordingly (see Appendix 5 for further details).

7.3 Lost to Follow-up

A subject will be considered lost to follow-up if the subject repeatedly fails to return for scheduled visits and is unable to be contacted by the trial site. The following actions must be taken if a subject fails to return to the clinic for a required trial visit:

- The site must attempt to contact the subject and reschedule the missed visit as soon as possible, counsel the subject on the importance of maintaining the assigned visit schedule and ascertain whether the subject wishes to and/or should continue in the trial.
- Before a subject is deemed lost to follow-up, the investigator or designee must make every effort to regain contact with the subject (where possible, 3 telephone calls, and if necessary, a certified letter to the subject's last known mailing address or local equivalent methods). These contact attempts should be documented in the subject's medical record.

• Should the subject continue to be unreachable, the subject will be considered to have discontinued from the trial.

8 TRIAL ASSESSMENTS AND PROCEDURES

Overview

The Schedule of Activities (Section 1.3) summarizes the frequency and timing of efficacy, PK, immunogenicity, pharmacodynamic/biomarker, safety, and other measurements applicable to this trial.

All assessments should be performed prior to trial treatment administration, unless otherwise indicated in the Schedule of Activities.

Blood collections for PK and pharmacodynamic assessments should be kept as close to the specified time as possible. Other measurements may be done earlier than specified timepoints if needed.

Additional serum or urine pregnancy tests may be performed, as determined necessary by the investigator or required by local regulations, to establish the absence of pregnancy at any time during the participation in the trial.

Instructions for the collection, handling, storage, and shipment of samples are found in the laboratory manual that will be provided. Collection, handling, storage, and shipment of samples must be as specified, and where applicable, under controlled temperature conditions as indicated in the laboratory manual.

8.1 Demography and Baseline Assessments

8.1.1 Demographics

Demographic details will be assessed at screening.

8.1.2 Diagnosis and Disease Status

A subject's history relating to the underlying disease including primary diagnosis, date of diagnosis, as well as disease status at trial entry, staging, and risk category will be recorded. The following should be recorded at screening:

The primary site of cancer, and initial and current disease stage (TNM staging system), will be recorded at screening.

For all subjects, record the PD-L1 status as per local assessment, if available.

For all subjects, record the dMMR or MSI status as per local assessment, if available.

The following should be recorded if available for subjects with the following types of cancer:

- Breast cancer: HER2, ER, and PgR status as per local assessment
- Ovarian: BRCA status as per local assessment
- HNSCC: HPV status in subjects with oropharyngeal disease as per local assessment

- NSCLC: the tumor mutational status including EGFR, ALK, KRAS, BRAF, MET, ROS1 genes or RET gene rearrangements or NTRK1/2/3 gene fusions as per local assessment
- Cervical cancer: HPV status as per local assessment

Additionally, if known, locally assessed cancer-associated mutations, gene signatures, and immune therapy prognostic targets may also be recorded.

8.1.3 Medical History

Any medical condition (signs, symptoms, and diagnosis) occurring prior to first dose of trial treatment should be documented in the source documents as medical history. Medical conditions that occur after the ICF is signed and prior to first dose of trial treatment should only be reported as AEs if they were assessed by the investigator to be caused by a protocol-mandated procedure (ie, tumor biopsy and/or CT scan), including wash-out or discontinuation of prior medications.

Any medical history/current medical condition that worsens after the first dose of trial treatment will be documented as an AE. See additional reporting details in Section 8.4 and Appendix 3.

Recording of prior therapies are detailed in Section 6.6, selected prior laboratory data in Section 8.3.6 and for prebaseline scans in Section 8.2.3.

8.2 Efficacy Assessments

Disease burden must be documented at screening and reassessed at each subsequent tumor evaluation. Response will be assessed by the investigator on the basis of physical examinations, CT scans and other modalities (eg, MRI, brain scans), using RECIST v1.1 (Eisenhauer et al., 2009), Appendix 7).

Importantly, in subjects who discontinue trial treatment without evidence of radiographic PD, tumor imaging must be performed until evidence of radiographic PD.

If the subject withdraws or is lost to follow-up, the data already collected and the data from the end of the trial visit will be kept.

8.2.1 Definition of Target and Nontarget Disease

Up to 5 target lesions (maximum 2 per organ) will be defined at screening and these must be followed throughout the trial. Biopsied tumor lesions or tumor lesions situated in a previously irradiated area, or in an area subjected to other loco-regional therapy, are not considered evaluable. For subjects with a single target lesion, it is mandatory to perform the imaging before taking the biopsy (both must be performed during the screening period). Biopsies cannot be taken from this single target lesion on-treatment unless approved by the sponsor medical monitor. Nontarget lesions will also be assessed throughout the trial.

Each lesion that is measured at baseline must be measured by the same method (either same imaging method or by photography, including a metric ruler) and when possible, the same local radiologist/physician throughout the trial so that the comparison is consistent.

Initial tumor imaging at screening must be performed within 21 days prior to the date of first dose. If a CT scan or MRI has been performed within 21 days prior to visit C1D1 as part of standard procedure, it is acceptable as a screening scan for the trial. Scans that exceed the 21-day window may be used for trial enrollment with sponsor approval. The site must review screening images to confirm the subject has measurable disease per RECIST 1.1.

8.2.2 Radiographic Assessments

Efficacy will be assessed based on imaging at screening and on treatment as described in Section 8.2.3.

Guidelines for on-trial imaging and process:

- All subjects will have imaging of the brain, thorax, abdomen, and pelvis performed during screening. Head and neck imaging is always required for subjects with HNSCC. Imaging of the pelvis is not required for subjects with HNSCC but is strongly recommended.
- Tumor imaging is strongly preferred to be acquired by CT with contrast. For the abdomen and pelvis, contrast-enhanced MRI may be used when CT with iodinated contrast is contraindicated, or when mandated by local practice. MRI is the strongly preferred modality for imaging the brain. Localized CT with contrast or MRI (with or without contrast; for sarcomas with contrast) must be acquired for assessment of lesions of the skeleton/extremities and head and neck if not visible on other images. At the discretion of the investigators and after approval of the sponsor, combined PET/CT (eg, FDG-PET) may be performed for tumor assessments as per RECIST 1.1, but only if the CT portion is of similar diagnostic quality to CT alone.
- The same imaging modality and ideally the same scanner should be used throughout the trial to optimize the reproducibility of the assessment and preserve the accuracy of the assessment of response or PD. Chest X-rays and ultrasound should not be used to measure tumor lesions.

8.2.3 Assessment of Disease Response and Progressive Disease

- On-trial imaging will be performed at Week 6 (-7 days), every 6 weeks (±7 days) for 50 weeks, and every 12 weeks (±7 days) thereafter from the date of first dose until PD is assessed by the investigator (unless the investigator elects to continue treatment and follow iRECIST beyond RECIST PD), the start of new anticancer therapy, withdrawal of consent, or death, whichever occurs first. Imaging assessments should follow calendar days and should not be adjusted for delays in cycle starts. If imaging shows PD, then a subsequent imaging assessment, in clinically stable subjects only, should be performed within 4 to 7 weeks to confirm PD if following iRECIST. Imaging is not required when subject is in survival follow-up.
- Imaging assessments should be scheduled using the date of first dose as the reference date (not the date of the previous tumor assessment) and should be respected regardless of whether trial treatment is temporarily withheld, or unscheduled assessments performed.
- The reading of the scans will be done by a local radiologist. To the greatest extent possible, sites should maintain the same radiologist throughout the trial. Results from the radiology

evaluations are to be recorded, and a copy of the evaluation reports should be kept in the subject's file. RECIST 1.1 criteria will be used for secondary endpoint response evaluation (Eisenhauer et al., 2009) and Appendix 7; iRECIST will be used for exploratory endpoint response evaluation (Seymour et al., 2017).

- Additional CT or MRI scans may be performed at the investigator's discretion to confirm response or new symptoms. Tumor imaging to confirm PR or CR should be performed at least 4 weeks after the first indication of a response is observed. In this case, the investigator must choose the imaging technology based on the clinical indication.
 - If an off-schedule imaging assessment is performed because progression is suspected, subsequent imaging assessments should be performed in accordance with the original imaging schedule.
 - Additional imaging assessments may be performed at any time during the trial at the investigator's discretion to support the efficacy evaluations for a subject, as necessary. Clinical suspicion of PD at any time requires a physical examination and imaging assessments to be performed promptly rather than waiting for the next scheduled imaging assessment.
- Sites will be required to submit electronic copies of prebaseline scans (since failure of last prior therapy, as available) and all subsequent scans on an ongoing basis to a centralized imaging CRO for exploring the tumor growth and possible independent review of disease assessments for subjects enrolled. Images obtained at an unscheduled timepoint should be captured in the eCRF and submitted to the central imaging vendor for subjects enrolled in the Expansion part.
 - Imaging data will be centrally collected and checked for quality by an imaging CRO designated by the sponsor. The local investigator's assessment will be used as primary for the endpoint analyses and for treatment decision making. Central review of the imaging data may be performed if deemed necessary.

8.2.4 *iRECIST* Assessment of Disease

For subjects who continue trial treatment beyond initial RECIST-defined PD, efficacy assessments must continue.

iRECIST is based on RECIST 1.1 but has been modified to account for the unique response patterns observed with immunotherapy. In this trial, iRECIST will be evaluated as an exploratory endpoint (Seymour et al., 2017).

iRECIST PD should be confirmed within 4 to 7 weeks after the first radiologic evidence of PD in clinically stable subjects. Subjects who have unconfirmed PD may continue on-trial treatment until PD is confirmed as long as the subject is clinically stable and has provided written informed consent prior to receiving additional treatment. Subjects who are clinically stable must meet the following criteria:

- Subject must have clinical benefit from continuation of trial treatment (as assessed by the investigator) and must not have rapid PD
- Subject is tolerating trial treatment
- Subject must have a stable ECOG status
- Treatment beyond PD will not delay an imminent intervention to prevent serious complications for PD (eg, CNS metastases requiring immediate treatment).

Any clinically unstable subjects should be discontinued from trial treatment at the first occurrence of radiographic PD. Subjects that are clinically unstable are not required to have repeated imaging to confirm PD by iRECIST; however, a confirmation of progression scan may be obtained at the investigator's discretion after consultation with the sponsor.

If repeat imaging shows iRECIST iCPD, subjects will discontinue trial treatment. However, if the subject is deriving benefit after iCPD is observed, an exception to continue trial treatment must be approved by the sponsor medical monitor. If repeat imaging shows iRECIST iSD, iRECIST iPR, or iRECIST iCR, imaging should be continued every 6 weeks (±7 days) and the subject should continue on trial treatment. Subjects who have repeat imaging to confirm PD do not need to undergo the next scheduled tumor imaging if it is less than 4 weeks later.

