4 TRIAL DESIGN

4.1 Description of Trial Design

This is a FIH phase 1/2a open-label, multicenter, multinational trial in subjects with non-CNS metastatic or advanced solid tumors for whom there is no available standard therapy likely to confer clinical benefit, evaluating the safety, tolerability, preliminary antitumor activity, PK, pharmacodynamics, and immunogenicity of GEN1053 as monotherapy as well as in combination with IM.

The trial will be conducted with a Dose Escalation part (phase 1a and 1b) and an Expansion part (phase 2a) as follows:

- Phase 1a Monotherapy Dose Escalation
- Phase 1b Combination therapy Dose Escalation
- Phase 2a Expansion

The Dose Escalation part will explore the safety of escalating doses of GEN1053 as monotherapy (phase 1a) as well as escalating doses of GEN1053 when combined with a fixed dose of an IM (phase 1b) in a sequential approach in a population of subjects with various solid tumors.

The sponsor will share relevant monotherapy safety data from phase 1a with the health authorities and submit a substantial amendment before initiating the combination Dose Escalation phase 1b.

The Expansion part is planned to provide additional safety and initial antitumor activity information of the RP2Ds for GEN1053 monotherapy and GEN1053+IM combination therapy, respectively, in selected tumor indications. In the first Expansion cohort (HNSCC), more detailed data related to the MoA of GEN1053 monotherapy will be generated. Upon PD while on GEN1053, and provided that the RP2D for the combination has been determined in phase 1b, subjects will have the option to cross over to GEN1053+IM to explore the effect of sequencing the trial treatments. In the second Expansion cohort, GEN1053+IM will be evaluated in subjects with NSCLC.

Each part will consist of a screening period (up to 21 days prior to C1D1), a treatment period (C1D1 until discontinuation of trial treatment), and 2 safety follow-up visits 30 days and 60 days after each subject receives the last dose of trial treatment, preceding the survival follow-up. Subjects will be treated in cohorts, defined as a group of subjects allocated to the same treatment.

Both GEN1053 and IM will per default be administered as an IV infusion in 3-week (ie, 21-day) cycles (Q3W) (refer to Section 6, Trial Treatment) until PD, unacceptable AE, or withdrawal of consent (refer to Section 7.1).

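### Section 8.2 requires imaging to PD after treatment stops without PD, but Section 8.2.3 waives all imaging in survival follow-up, so DoR and PFS could be censored informatively

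*Combined protocol and SAP*

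**What the plan says.** **Imaging.** Section 8.2 states that "in subjects who discontinue trial treatment without evidence of radiographic PD, tumor imaging must be performed until evidence of radiographic PD". Section 8.2.3 sets the schedule from the date of first dose: a Week 6 scan, then "every 6 weeks (±7 days) for 50 weeks, and every 12 weeks (±7 days) thereafter". Imaging runs until investigator-assessed PD (with an exception for subjects followed by iRECIST beyond PD) or "the start of new anticancer therapy, withdrawal of consent, or death, whichever occurs first". Stopping treatment is not on that list. The same bullet then ends: "Imaging is not required when subject is in survival follow-up". Section 8.2.2 describes the scope differently again: "Efficacy will be assessed based on imaging at screening and on treatment as described in Section 8.2.3".

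**Survival follow-up.** Section 4.1 provides for "2 safety follow-up visits 30 days and 60 days after each subject receives the last dose of trial treatment, preceding the survival follow-up". Section 7.1.2 has survival status checked every 12 weeks, "beginning from the day the subject receives the last trial treatment administration". Section 7.1.1 moves a subject into survival status follow-up once new anticancer treatment starts. In the Schedules of Activities (Tables 1-1 and 1-9), survival follow-up is a column after the two safety visits, and the CT/MRI row only points back to Section 8.2.

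**Endpoints.** DoR (Section 9.4.2.1.2) counts first PD or death in confirmed responders and is censored and summarised like PFS. PFS (Section 9.4.2.2.3) is estimated by Kaplan-Meier and censored according to an external guidance table that the protocol does not reproduce.

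**The concern.** Consider a subject who stops for an adverse event, has no radiographic PD and starts no new therapy. Section 8.2 says this subject must be scanned to PD. Once the subject is in survival follow-up, Section 8.2.3 says scans are not required. Neither sentence mentions the other, and the Schedules of Activities send the site back to the section that contains both.

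Such subjects are foreseeable. Section 7.1 lists unacceptable adverse events, clinical progression and subject request among the reasons to stop treatment, and Sections 6.7.1 and 6.7.2.4 add DLTs and further safety stopping rules. Section 4.4.2 estimates about 6 months of treatment and about 11 months of survival follow-up, so the conflict covers much of a subject's time on trial.

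If scanning ends when a subject leaves treatment for toxicity, censoring of DoR and PFS may be related to prognosis. Kaplan-Meier assumes that it is not. Scans that were not taken cannot be recovered at analysis.

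**Working it through.** The plan states no figure on this point, so there is none to reproduce. The check is a reading of the text, a count of scans, and an illustration.

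**1. Which rule applies, and when?** For the subject described above:

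| Source | Imaging after last dose |
|---|---|
| Section 8.2 | Mandatory until radiographic PD |
| Section 8.2.3, end-of-imaging list | Continues; stopping treatment is not an end point |
| Section 8.2.3, closing sentence of the bullet | Not required in survival follow-up |
| Section 8.2.2 | Describes on-treatment imaging only |

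The outcome turns on when survival follow-up starts. Section 4.1 puts it after the 60-day visit, and Section 7.1.2 sets a 12-week clock from last dose. Neither depends on PD. Section 7.1.1 depends on new therapy, which this subject has not started. So, at the latest when survival follow-up starts after the 60-day visit, the mandatory rule and the waiver both apply to the same subject.

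**2. Scans at stake.** Inputs: 21-day cycles, so last dose falls on day 21k; nominal 6-weekly scans on days 42, 84, ..., 336, then every 84 days.

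- Imaging to PD (Section 8.2): all scans.
- Imaging ends 60 days after last dose (Section 4.1 start): 1 scan in the 6-weekly phase, 0 to 1 in the 12-weekly phase.
- Imaging ends at last dose: 0 scans.

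**3. Response confirmation.** Confirmation needs at least 4 weeks (28 days) after the first response scan. In the 6-weekly phase, the single post-treatment scan falls 21 or 42 days after last dose. If it is the first to show response, confirmation is possible from day 21 + 28 = 49, before day 60, or from day 42 + 28 = 70, after it. So a confirmation can be missed but need not be. The Section 9.5 success rule uses confirmed ORR, with cut-offs of 6/40 and 9/40 in Table 9-3.

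**4. Illustration of bias in median DoR.** All inputs here are assumptions and none comes from the documents. On-treatment PD is exponential with median 6 months, so λ = ln 2 / 6 = 0.1155 per month. A share q of responders stops without PD, with stopping hazard μ = λq/(1 − q). The PD hazard after stopping is HR × λ. Each scenario uses 400,000 simulated responders with exact event times. Excess = median with imaging cut short − median with imaging to PD.

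| q | HR | To PD (months) | Ends at +60 days (excess) | Ends at last dose (excess) |
|---|---|---|---|---|
| 10–40% | 1 | 5.99–6.01 | 5.99–6.01 (0) | 5.99–6.01 (0) |
| 10% | 2 | 5.83 | 5.89 (0.06) | 6.00 (0.17) |
| 20% | 2 | 5.63 | 5.75 (0.12) | 6.00 (0.37) |
| 40% | 2 | 5.22 | 5.43 (0.21) | 6.01 (0.79) |
| 40% | 3 | 4.81 | 5.05 (0.24) | 6.01 (1.20) |

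There is no bias when the hazard is unchanged after stopping. The bias is upward when the hazard rises.

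**The case against.** The best defence is that the protocol, read as a whole, already favours continued imaging. Section 8.2 uses mandatory language for exactly these subjects, while Section 8.2.3 is only permissive. The end-of-imaging list omits stopping treatment. Section 7.1 wants subjects who are off treatment to stay on trial and continue efficacy evaluations. Section 7.1.1 links survival follow-up to new therapy, which is itself an imaging end point. On this view, the waiver was meant for subjects already past such a point.

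That is probably the intent, and it shows which way to resolve the conflict. It does not remove it. The waiver is unqualified, Section 8.2.2 speaks only of on-treatment imaging, and Sections 4.1 and 7.1.2 admit subjects to survival follow-up without regard to PD. The schedules record new anticancer treatment at survival visits, but this settles nothing, because subjects past PD would need that row too.

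The defence does succeed against two stronger readings. A reader might infer from Section 7.1.2 that imaging may lapse on the day of last dose. That wording more naturally anchors a 12-week clock, and both Section 4.1 and the schedules put the safety visits first. A reader might also infer that an unconfirmed response at discontinuation is necessarily lost. Section 8.2.3 separately calls for confirmatory imaging, and four weeks can fit inside the 60-day period.

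**Conclusion.** The contradiction is real and wrong as written for a subject who stops without radiographic PD and starts no new therapy. It leaves sites free to follow different rules, at the latest from the start of survival follow-up after the 60-day visit.

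The statistical consequence is possible, not certain. It needs sites to act on the waiver and PD risk to change after stopping. If that risk rises, DoR and PFS are overstated; if it is unchanged, they are not biased. A reader might want to state what share of DoR observations would be cut short. The documents do not support any such figure: they give no rate of stopping without PD, and the external censoring table is not reproduced, so even the censoring date cannot be confirmed. The excess of 0 to 0.24 months with imaging ending at 60 days rests wholly on the assumed inputs. The 1.20-month figure applies only if imaging ended at last dose, which is not the better reading.

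The stakes are also bounded. DoR is secondary, PFS is exploratory, and Section 9.1 plans no confirmatory testing. The effect is on estimates and, through a missed confirmation, possibly on confirmed ORR.

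**What to change.** Replace the waiver sentence in Section 8.2.3 with wording such as: *Subjects who stop treatment without radiographic PD remain on the Section 8.2.3 imaging schedule, through safety and survival follow-up, until radiographic PD, a new anticancer therapy, consent withdrawal or death. Imaging is not required after one of these.* Leave the existing iRECIST exception in place.

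Then align:

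- **Section 8.2:** add the same end points. It currently has no exception for new therapy, whereas Section 8.2.3 stops imaging there.
- **Section 8.2.2:** change the scope from on treatment to on trial.
- **Sections 7.1.1 and 7.1.2:** state one start point for survival follow-up, consistent with Section 4.1.
- **Schedules of Activities:** carry the rule in the CT/MRI row.

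The SAP is to be finalised before database lock, so it can also write out the censoring rules and add a sensitivity analysis for subjects whose imaging ends without PD.

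The cost is amendment wording and a site notice. No scan is added beyond those Section 8.2 already requires.
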